4. ANALYSIS POPULATIONS

The three analysis populations for this study are defined below. Identification of the subjects to be included in each analysis population will be determined prior to database unblinding. The database will be locked and unblinded after the SAP is signed and authorized, there are no outstanding data issues, and the final analysis populations are imported into the study database.

4.1.1 Safety Population

All subjects who are randomized and receive at least one dose of study medication will be included in the Safety Population. The Safety Population is the primary analysis population for safety assessments. Results will be presented “as treated.”

4.1.2 Full Analysis Set (FAS) Population

All subjects who are randomized, receive at least one dose of study medication, and had one or more post-Baseline on-treatment primary efficacy assessment(s) will be included in the FAS Population. The FAS Population is the primary analysis population for clinical efficacy. Results will be presented “as randomized.”

4.1.3 Per Protocol (PP) Population

All subjects who are in the FAS population and who do not have any major protocol deviations will be included in the PP Population. The PP Population will be used as a sensitivity analysis for clinical efficacy.

4.2 Disposition of Subjects

Subject accountability will be summarized based on all subjects enrolled into the study by treatment sequence. The following patient accountability information will be presented:

- The number and percentage of subjects who enrolled in the study, who were randomized, who completed the study, and who prematurely discontinued from the study
- The number and percentage of subjects who discontinued prematurely, by reason for premature discontinuation
- The number and percentage of subjects in the Safety, FAS, and PP populations

In addition to these summaries, a listing by patient will be provided that shows treatment, subject number, sex, age, race, reason for discontinuation, and any specific comments related to discontinuation.

4.3 Protocol Deviations

Protocol deviations will be jointly assessed by the sponsor and Rho and summarized by treatment sequence and overall. The final protocol deviation listing for the study (prior to unblinding) will be approved by the sponsor.

Protocol deviations will be categorized into, but not limited to, the following protocol deviation categories and will be classified as major or minor:

- Prohibited Medication/Therapy
- Dosing or Randomization Error
- ICF/Consent Process
- Eligibility Criteria Not Met
- Missed Study Procedure: Efficacy or Safety Assessment
- Unreported AEs/SAEs
- Other Protocol Deviation (not otherwise defined)

5. DEMOGRAPHIC AND OTHER BASELINE CHARACTERISTICS

5.1 Demographics and Baseline Characteristics

Demographics and baseline characteristics including age, sex, race, weight and height will be summarized by treatment sequence and overall on the safety, FAS, and PP populations.

5.2 Prior and Concomitant Medications

Prior medications are medications that were taken prior to the first dose of study medication. Concomitant medications are medications that were taken during the treatment period.

Medications with partial start dates will be determined as concomitant medications by using available non-missing information. Completely missing start dates (i.e. missing information for medication start day, month, and year) are assumed to be concomitant medications.

Missing end dates for prior and concomitant medication will be imputed based on the following rules:

- If only the year is known, the date will be set to 31 December of that year. If the year is the same as the treatment start date, the date will be set to the treatment end date.
- If the year and month are known the date will be set to the end of the specified month.
- If the end date is completely missing it will be assumed that the medication is ongoing for the duration of the study, and as such regarded as concomitant.
- If these rules are followed and the completed end date is after the last visit date, the end date will be set to the last visit date.

The frequency of subjects using prior and concomitant medications at any stage of the study will be summarized according to WHO-DD Version 2018.01 Anatomical Therapeutic Chemical (ATC) level 2 and level 4, by treatment on the Safety Population. The ATC levels will be presented in decreasing order of the total number of subjects (frequency) who used each medication. The ATC levels with the same frequency will be presented alphabetically.

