2.5 Method of Assigning Subjects to Treatment

Subjects who satisfy the inclusion/exclusion criteria will undergo a 7-day washout of previous ADHD stimulant medications, and AR19 or placebo will then be initiated at 10 mg/day the morning after Visit 2. Depending on treatment group, the daily dose will be increased in 10-mg increments every week to 20 or 40 mg/day. The study duration from first dose of study drug to the follow-up visit is expected to be approximately 6 weeks.

Subjects will be monitored for safety and for therapeutic response to AR19 treatment. Safety and clinical response assessments will be performed at each visit or more frequently if clinically indicated.

Each subject must meet all the inclusion criteria and none of the exclusion criteria to be eligible for enrollment in the study. Waivers to inclusion/exclusion criteria will NOT be granted.

Randomization will occur via Interactive Web Response System (IWRs) at Visit 2, if a subject meets all inclusion and no exclusion criteria. Subjects will be randomized 1:1:1 to placebo or 20 or 40 mg AR19/day. Randomization will take place according to a fixed schedule using a permuted block design with no stratification by clinical site.

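### SAP 5.2 classes a medication with a wholly missing start date as concomitant even when its recorded stop date is before the first dose

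*SAP*

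**What the plan says.** SAP 5.2 gives two definitions. "Prior medications are medications that were taken prior to the first dose of study medication", and "Concomitant medications are medications that were taken during the treatment period". A drug begun before the first dose and continued afterwards meets both.

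The section then sets date rules.

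- Start date wholly unknown: "Completely missing start dates (i.e. missing information for medication start day, month, and year) are assumed to be concomitant medications".
- Start date partly known: "Medications with partial start dates will be determined as concomitant medications by using available non-missing information".
- Stop date known to month and year: the last day of that month is used.
- Stop date known to the year only: 31 December of that year is used, with one exception. "If the year is the same as the treatment start date, the date will be set to the treatment end date".
- Stop date wholly missing: the drug is treated as ongoing and so as concomitant.
- An imputed stop date later than the last visit is pulled back to the last visit.

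The first rule sets no condition on the stop date. The stop-date rules deal only with incomplete dates. The result is a count of subjects by ATC level 2 and level 4 within each treatment group, on the Safety Population.

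For context, SAP 2.5 states that eligible subjects "will undergo a 7-day washout of previous ADHD stimulant medications". Protocol 5.9.1 requires non-study stimulants to have been stopped at least 7 days before Baseline. Protocol Appendix B lists stimulants as a prohibited class, and SAP 4.3 has a deviation category named "Prohibited Medication/Therapy".

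**The concern.** Whether a drug was in use on treatment depends on whether its use had ended by the first dose. Once a stop date before the first dose is known, the start date adds nothing. The missing-start rule nevertheless decides the class from the start date alone and overrides the stop date.

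The type of record it misclassifies is plausible here. The stimulant washout requirement turns on the stop date, so a site has a reason to obtain that date. The requirement does not depend on when the stimulant was begun. A record with a stop date and no start date can arise for an earlier ADHD stimulant. Under the written rule it would appear in the medication table as on-treatment use of a prohibited stimulant, in a placebo-controlled trial of a stimulant, when no such use took place.

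**Working it through.** The plan states no figure on this point, so there is nothing to reproduce. The check applies the SAP 5.2 rules as written.

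**Logic.** For any record, start ≤ stop. If stop < first dose, then start < first dose, and the whole period of use lies before treatment. By the section's definitions the drug is prior only. The missing-start rule calls it concomitant.

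**Inputs.** A stimulant is stopped 7 days before Baseline (the minimum in Protocol 5.9.1). The first dose is on the morning of Day 2 (Protocol 6.1.2). The stop is therefore 7 + 1 = 8 days before the first dose.

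**Assumed calendar, for illustration.** Baseline (Day 1) is 17 October 2018, so the stop is 10 October, the first dose is 18 October, and the end of treatment (Day 36) is 17 October + 35 days = 21 November. The first four rows below are this one drug with its stop date recorded ever less completely. The last two rows are drugs stopped in an earlier month and an earlier year.

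| Stop date as recorded | Stop date used | Start wholly missing | Start known or partial, before first dose |
|---|---|---|---|
| 10 October 2018 | 10 October 2018 | concomitant | prior only |
| October 2018 | 31 October 2018 | concomitant | concomitant |
| 2018 | 21 November 2018 | concomitant | concomitant |
| missing | ongoing | concomitant | concomitant |
| September 2018 | 30 September 2018 | concomitant | prior only |
| 2017 | 31 December 2017 | concomitant | prior only |

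The two right-hand columns differ in rows 1, 5 and 6. In those rows the stop date, full or partial, is enough to place the end of use before the first dose, and only the missing-start rule makes the drug concomitant. In rows 2 to 4 the stop-date rules give that result whatever the start date, so the missing-start rule changes nothing.

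**How often a month-and-year stop date can be placed before the first dose.** For a stop on day s, the first dose is on s + 8. The imputed month end falls on or after the first dose when s is at least 8 days before the end of its month. The last 8 days of each month fail this test: 12 × 8 = 96 of 365 dates. For the other 365 − 96 = 269 dates (269/365 = 74%), the month-end rule itself makes the drug concomitant. For the 96 dates (96/365 = 26%), the month end is before the first dose and the missing-start rule is what misclassifies. These shares assume a stop exactly 7 days before Baseline and Baseline visits spread evenly over a 365-day year. They describe how the rules behave and do not estimate a count in this trial.

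**After the fix.** Rows 1, 5 and 6 become prior only in both columns. Rows 2 to 4 stay concomitant.

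**The case against.** Defaulting unknown dates towards on-treatment is a recognised conservative choice, and the SAP takes the same line in section 8.1, where an adverse event with no start date is dated to the first dose. That argument stands where the stop date is missing or too vague. It does not reach a drug whose stop date is known to precede the first dose, because nothing about its timing relative to treatment is then uncertain.

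Three stronger readings are tempting, and the documents do not support them.

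- *Washed-out stimulants in general will be reported as concomitant.* The rule needs day, month and year of start all to be missing. With even a partial start date before the first dose and a full stop date before it, the drug stays prior. Neither document says how many records lack a start date, or that long-used stimulants are especially likely to. The number could be zero.
- *Per Protocol membership is affected.* SAP 4.3 has the sponsor and its contractor assess deviations together, with the listing approved before unblinding. No text makes the SAP 5.2 class an input to that assessment, and SAP 3 provides for by-subject listings of all study data.
- *The stop-date rules are wrong too.* They can carry a drug stopped shortly before Baseline past the first dose, as rows 2 and 3 show. But there the recorded date does not settle the matter. Changing that default would reduce false on-treatment use at the risk of missing real use, which is a trade-off and not an inconsistency.

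**Conclusion.** The point holds as a minor drafting defect. The missing-start rule in SAP 5.2 contradicts the definition of concomitant use in the same section whenever the recorded stop date, or its available parts, places the end of use before the first dose. A stopped drug, such as a washed-out stimulant with no recorded start date, can then be counted as concomitant.

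The effect is confined to the descriptive summaries of prior and concomitant medications. No efficacy estimate uses the classification. The number of affected records cannot be derived from the documents. The conclusion assumes that the rule is programmed as written; a programmer who checked the stop date first would avoid the error, but the SAP does not say to do so.

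**What to change.** Add one sentence to SAP 5.2, to this effect: a medication whose recorded stop date, or whose available stop-date parts, shows that use ended before the first dose of study medication is prior only, whatever its start date. Keep the concomitant default for a missing start date when the stop date is missing or cannot be placed before the first dose.

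The existing stop-date rules can stay as they are. Applying them first and comparing the result with the first dose gives the intended class in every row of the table. A further rule for drugs stopped because of the washout is not proposed, since neither document describes a data field that records that reason for non-study medications.

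The cost is one sentence and one extra condition in the derivation, with no new data. It should be made before the SAP is finalised, which Protocol 9.2 requires to happen before unblinding.

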5.3 Medical History

Medical history findings will be coded using MedDRA 21.0 and will be summarized descriptively by treatment on the Safety Population.

6. MEASUREMENT OF TREATMENT COMPLIANCE

Compliance rates will be calculated by dividing the number of doses taken by the number of doses that should have been taken during the treatment period and will be summarized by treatment group.

Compliance will be further categorized and summarized by treatment group as follows:

- <80%.
- 80% to 100%.
- >100%.

7. EFFICACY EVALUATION

7.1 Overview of Efficacy Analysis Issues

7.1.1 Handling of Dropouts or Missing Data

Missing data could occur under either or both of the following scenarios: (1) missing or invalid data for individual questions in the AISRS; and (2) missing AISRS total scores at individual visits. The approach to handling missing data under these scenarios is described below.

7.1.1.1 Missing Individual Items in the AISRS Scale

The AISRS is a validated 18-item scale that corresponds directly to the 18 ADHD items in the Diagnostic and Statistical Manual of Mental Disorders. It includes adult prompts for each item. The AISRS will be used to determine trial eligibility. An AISRS assessment will be completed at Study Visits 1 through 7. The Investigator or other designated, qualified individual from the study research team will complete the assessment.

Missing or invalid data for individual questions will be handled by rules specified as follows:

- If 4 or more individual items in the AISRS have missing or invalid data, the AISRS total score will be set to missing.
- If 3 or less individual items in the AISRS are missing or invalid, the values for the missing individual items will be imputed using the mean of the non-missing individual items for the particular subject at that visit, rounded up to the nearest integer.
- If any item within an AISRS subscale is missing or invalid, the entire subscale score will be set to missing.

7.1.1.2 Missing AISRS Total Scores at Individual Study Visits

Primary Analysis

No imputation of missing AISRS total scores at individual visits will be done for the primary efficacy analysis. The mixed model repeated measures methods used to analyze the primary endpoint has been designed to utilize all available data and provides valid estimates under the assumption of data which are missing completely at random or missing at random. Accordingly, all subjects with one dose of study medication and at least one post-baseline on-treatment assessment of the primary efficacy variable will be included in the model.

Sensitivity Analyses

To explore the sensitivity of the primary analysis results, analyses using two imputation methods may be performed: a placebo-based multiple imputation (MI) pattern-mixture model (PMM) analysis and a tipping point analysis using the PMM. If the dropout rate in this study is <2%, these sensitivity analyses will not be performed. This decision will be made prior to database unblinding.

Sensitivity analysis one: Placebo-based MI PMM

To explore the robustness of the primary analysis results, a sensitivity analysis will be carried out that assesses the situation where the data are not missing at random (NMAR). More specifically, all subjects taking AR19 who discontinue for any reason will be assumed to behave like placebo subjects.

A controlled, multiple imputation approach based on PMM will be applied for those subjects on AR19 using the 'Copy Reference' approach [3]. More specifically, missing data for those subjects taking AR19 who discontinued early will be imputed based on the posterior distribution of the placebo group. Missing data for placebo subjects who discontinue early will also be imputed using the observed

values of the placebo group.

Data will be imputed using SAS PROC MI (v9.3 or later) using the full conditional specification method (FCS). Twenty burn-in iterations will be performed prior to each imputation. The imputation model will include observed non-missing AISRS scores, baseline AISRS score, age, and sex. One hundred imputed datasets will be generated for analysis.

The same model used in the primary analyses will be fit to each of the 100 datasets. The parameter estimates and standard errors will be combined using PROC MIANALYZE in SAS v 9.3 or higher.

Sensitivity analysis two: Tipping Point Analysis using PMM

The goal of the tipping point analysis is to determine how robust the results of the primary analysis are to varying its assumption that the change from baseline at Visit 7 AISRS total scores for subjects that discontinue early from the AR19 group is the same as the completers in the AR19 group. In particular, this analysis examines how altering this assumption to allow the discontinued subjects to have better and worse outcomes will impact the resulting estimates of the treatment effect. This will quantify the range of values which the assumptions can take on and still provide the same conclusions as the primary analysis, giving a very direct measure of the sensitivity of the primary analysis to deviations from the assumptions using an approach that has missing values for AR19 discontinuation subjects imputed. Missing AISRS total score data in the AR19 group will be imputed based on observed values in the AR19 group and likewise, missing AISRS total score values in the placebo group will be imputed based on observed values in the placebo group.

In this analysis, the estimate of the effect in the AR19 subjects may be viewed as a weighted average of the observed average for AR19 completers and the average MAR estimate for AR19 subjects. Shift values of .05 (treated subjects have 5% of the change from baseline AISRS total score as assumed in the primary methodology) through 1 (treated subjects have 100% of the change from baseline AISRS total score as assumed via the primary methodology) will be applied at increments of .05 and reported. The primary analysis will be rerun for all shift values and the resulting treatment difference, 97.5% CI and p-value for each shift value will be reported; the wider the range of values that result in no change in interpretation, the more robust the analysis results may be considered to be.

Subjects receiving placebo who discontinue prior to the end of the treatment period will have their change from baseline AISRS total score value imputed

based on the assumption that they respond to treatment in a similar manner to the placebo subjects who completed the study. For subjects receiving AR19 who discontinue prior to the end of the treatment period, the assumed response to treatment will be examined in increments from worst (subjects respond in a similar manner to the placebo subjects who completed the study) to best (subjects respond in a similar manner to the AR19 subjects who completed the study).

The steps to implement the tipping point analysis are as follows:

- 1) A mixed model repeated measures (MMRM) model will be run using all observed data and the LS mean in the AR19 group (20 and 40 mg/day separately) of change from baseline at Week 7 in AISRS total score will be calculated.
- 2) Missing data will be imputed based on the MAR assumption using multiple imputation procedure (PROC MI) to create 100 complete datasets with 20 burn-in iterations.
- 3) For subjects in the AR19 dose groups, the imputed values from Step 2 will be “penalized” by adding a percentage (i.e. 5%, 10%, 15%, 20%, etc. of the LS mean treatment difference) of the absolute value of the mean change calculated from Step 1; for the placebo group, no “penalty” will be taken for the imputed values.
- 4) Each newly generated complete dataset from Step 3 will be analyzed using the primary analysis MMRM model and results from all 100 datasets will be combined (PROC MIANALYZE) to generate inferences.
- 5) This analysis (Steps 3-4) will be repeated for a range of values (i.e. 5%, 10%, 15%, 20%, etc. of the treatment difference) until either the tipping point (where statistical significance of the treatment effect is lost) is identified or the 100% penalty is applied.

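### SAP 7.1.1.2 gives the tipping-point penalty two bases that disagree, and the SAP 7.4.1 estimand does not describe what the primary MMRM estimates

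*SAP*

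**What the plan says.** All of the tipping-point text is in SAP 7.1.1.2.

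- The description promises an analysis "altering this assumption to allow the discontinued subjects to have better and worse outcomes". It then sets a grid of retained fractions: "Shift values of .05 (treated subjects have 5% of the change from baseline AISRS total score as assumed in the primary methodology) through 1", where 1 is the primary assumption. On reporting it is explicit: "The primary analysis will be rerun for all shift values and the resulting treatment difference, 97.5% CI and p-value for each shift value" are all to appear.
- The same description bounds the AR19 dropouts between "worst (subjects respond in a similar manner to the placebo subjects who completed the study") and a best case like AR19 completers.
- Step 1 calculates the LS mean change in each AR19 dose group, at Week 7. It calculates no difference from placebo.
- Step 3 has an unrestricted scope ("For subjects in the AR19 dose groups, the imputed values from Step 2 will be" made worse). The amount is set, in that sentence, "by adding a percentage (i.e. 5%, 10%, 15%, 20%, etc. of the LS mean treatment difference) of the absolute value of the mean change" found in Step 1. Placebo takes no penalty.
- Under Step 5 the penalised analysis "will be repeated for a range of values (i.e. 5%, 10%, 15%, 20%, etc. of the treatment difference"), which names the difference again. The loop has its own stopping rule and goes on "until either the tipping point (where statistical significance of the treatment effect is lost) is identified or the 100% penalty is applied".

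SAP 7.4.1 closes with an estimand defined in randomised subjects who stay in the study to the end of blinded treatment, whatever their adherence. The same section runs the MMRM on the FAS with all available data. SAP 4.1.2 and the primary-analysis text of 7.1.1.2 admit any dosed subject with one on-treatment post-baseline AISRS.

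**The concern.** A tipping-point result is a statement about how large a penalty the conclusion survives, so it means nothing until the unit of the penalty is fixed. Here the programmer must choose between a percentage of the treatment difference and a percentage of the AR19 improvement. The two coincide only if placebo does not change. If the choice is made after unblinding, it can decide whether the report says that significance is lost or that it holds throughout.

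Four smaller conflicts sit in the same text. The retained-fraction grid runs in the opposite direction to Step 5, and can go beyond the stated worst case. The description reports all shift values, while Step 5 stops at the tip. Better outcomes are announced, but Step 3 only adds penalties. Step 1 says Week 7, where the endpoint is Visit 7 (Week 5).

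The estimand sentence is a separate matter. It would let the report present a result for all FAS subjects under missing at random (MAR) as an effect among those who stayed.

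**Working it through.** **Inputs.** SAP 2.7: difference 7.0, SD 13.0, alpha 0.025, 87 per group for about 90% power, 104 randomised per group, 20% dropout. SAP 3: two-sided tests. SAP 7.2.1: a higher AISRS is worse, so adding points is a penalty. The AR19 improvement x is not in the documents; 8, 12 and 15 points are assumptions.

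**The plan's own figure.** 7 / (13 × √(2/87)) = 7 / 1.971 = 3.551. Subtracting 2.2414 leaves 1.310, a power of 0.905 (0.900 with the exact t). The stated 90% reproduces, and it is two-sided.

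**Penalty needed to tip at 20% dropout.** Evaluable per arm: 104 × 0.8 = 83.2. SE = 13 × √(2/83.2) = 2.016. Critical difference = 2.2414 × 2.016 = 4.52. A penalty of P points on the AR19 dropouts leaves an effect of 7 − 0.2P. Setting this to 4.52 gives P = 12.4 points. The SE is held fixed as the penalty grows.

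| Penalty at 100% | Points | Effect | p |
|---|---|---|---|
| Treatment difference | 7 | 5.6 | 0.0055 |
| Mean change, x = 8 | 8 | 5.4 | 0.007 |
| Mean change, x = 12 | 12 | 4.6 | 0.022 |
| Mean change, x = 15 | 15 | 4.0 | 0.047 |

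On the difference basis the tip lies at 12.4/7 = 177%, beyond the 100% stop. On the mean-change basis it is reached once x exceeds 12.4. Simulated multiple imputation puts that threshold at about 12 to 13, with x = 12 borderline (p 0.019 to 0.027). At x = 15 a penalty labelled 50% is 3.5 points on one basis and 7.5 on the other.

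**Lower dropout.** At 16.3% (87 of 104 retained) the SE is 1.971 and the threshold for x is (7 − 2.2414 × 1.971)/0.163 = 15.8. At 10% the SE is 1.900 and the threshold is 27.4.

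**How often the verdicts differ.** The table gives the share of trials with a significant primary result in which one basis tips by 100% and the other does not. Simulation: five visits, SD 13, visit correlation 0.4 to 0.8 at 20% dropout and 0.6 otherwise, 100 imputations, 5,000 trials per scenario.

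| Dropout | x = 8 | x = 12 | x = 15 |
|---|---|---|---|
| 20% | 7–8% | 27–29% | 43–44% |
| 16.3% | 6% | 20% | 33% |
| 10% | 3% | 10–11% | 17% |

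Most trials agree in every cell.

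**The retained-fraction grid.** Keeping a fraction f of the change is, for the means, a penalty of (1 − f)x, which is the complement of the mean-change basis. Placebo-like is f = (x − 7)/x: 0.125, 0.42 and 0.53 for x = 8, 12 and 15. So 2, 8 and 10 of the 20 grid values are harsher than the stated worst case.

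**Estimand.** The SAP sentence conditions on staying in the study, which is a post-randomisation outcome. The MMRM keeps later dropouts and, under MAR, estimates a Week 5 mean for all FAS subjects. Subjects who cannot tolerate their dose are withdrawn (SAP 2.6; Protocol 5.6). After the Early Termination visit no efficacy visit is scheduled (Protocol Table 6.1.1), and the follow-up call is for completers (Protocol 6.1.7). The model therefore projects dropouts from subjects who stay.

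**The case against.** The best defence is that the intended basis can be inferred. The parenthesis in Step 3, Step 5 and the worst case all point to the treatment difference, so this is a drafting repair. That is largely fair, and the fix adopts that basis. It does not remove the conflict, because Step 1 computes only the other quantity and Step 3 applies the percentage to it.

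It can also be said that the analysis is optional. SAP 7.1.1.2 says it may be performed, but rules it out only below 2% dropout, and the plan expects 20%.

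Three stronger readings are tempting and are not supported:

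- A reader might count three separate scales. For the means, the retained fraction is the mean-change basis with its label reversed, so there are two numerical bases.
- A reader might say that Step 3 leaves open which visits are penalised. It covers the imputed values from Step 2 without restriction. In simulation, penalising Visit 7 only or all later visits moved the Week 5 estimate by at most 0.04 points.
- A reader might treat a 100% difference penalty as equal to placebo. That holds only if the dropouts' imputed mean is close to the AR19 LS mean. If poorer responders leave, with an imputed mean 4.9 points worse (x = 15, placebo 8), dropouts improve by 15 − 4.9 = 10.1 before the penalty and 3.1 after it. That is 4.9 points worse than placebo.

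Finally, Copy Reference already covers a placebo-based assumption. That limits what is lost if the tipping-point analysis is unclear.

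**Conclusion.** The point holds, and should be fixed. As written, the penalty cannot be programmed in one way only, and the two bases can give opposite answers. At the planning values and 20% dropout, the treatment-difference basis does not tip by 100%, while the mean-change basis does if the AR19 improvement exceeds about 12 to 13 points. The conflict in the text is certain. Its effect on the conclusion is conditional on an improvement the documents do not state and on dropout near the planned rate; a reader should not infer that the verdict would usually flip.

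The estimand sentence does not describe the MMRM. It might be taken to show that the primary estimate is biased, but nothing in the documents shows that. The fault lies in what the estimate is said to represent. The primary test, its alpha and the Copy Reference analysis stand.

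**What to change.** Amend the SAP before unblinding.

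1. **Step 1.** For each dose, calculate the LS mean difference from placebo at Visit 7 (Week 5), D. This also corrects Week 7.
2. **Step 3.** Add k × |D| to all imputed values in that dose group, and nothing for placebo.
3. **Step 5.** Run k from 0 to 1 in steps of 0.05. Report the estimate, 97.5% CI and p-value at every k. The tipping point is the smallest k with p ≥ 0.025. If there is none, report that it was not reached at loss of the full estimated treatment difference.
4. **Label for k = 1.** Describe it as loss of the full treatment difference relative to MAR, not as equality with placebo completers. Show the resulting mean of the AR19 dropouts beside the placebo mean.
5. **Range.** If a tip is to be located above k = 1, state the maximum in advance. At the design values and 20% dropout it lies near k = 1.8.
6. **Tidying.** Delete the .05 to 1 retained-fraction grid or restate it as k. Drop the promise of better outcomes or add negative k.
7. **Estimand (SAP 7.4.1).** Restate it as the Week 5 mean difference had subjects continued in the study on assigned treatment through Week 5, estimated in the FAS under MAR. Say that this is a hypothetical handling of withdrawal, because subjects who stop treatment leave the study and have no later efficacy visits. Report by arm the number of randomised subjects outside the FAS.

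The cost is SAP wording and one changed loop in the planned code. Data collection, the primary model and alpha stay as they are.
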